**This section will ask you some questions about smoking. For the questions below, please try to select a single number.**

B2. Have you smoked at least 100 cigarettes (5 packs=100 cigarettes) in your entire life?

- Yes
- No ➔ Go to Question B6.
- Don't know / Not sure ➔ Go to Question B6.

B3. How many total years have you smoked (or did you smoke) cigarettes? Do not count any time you may have stayed off cigarettes.

\_\_\_\_\_ Years *If you smoked less than one year, write "1."*

B4. On average when you have smoked, about how many cigarettes do you (or did you) smoke a day?

A pack usually has 20 cigarettes in it.

\_\_\_\_\_ Number of cigarettes per day

B5. How long has it been since you last smoked a cigarette (even one or two puffs)?

*First check which one of the following choices applies to you. Then, if applicable, write a number on the line for how many days, weeks, months, or years it has been since your last cigarette.*

- I smoked a cigarette today (at least one puff).
- 1-7 days. ➔ Number of days since last cigarette: \_\_\_\_\_
- Less than 1 month. ➔ Number of weeks since last cigarette: \_\_\_\_\_
- Less than 1 year. ➔ Number of months since last cigarette: \_\_\_\_\_
- More than 1 year. ➔ Number of years since last cigarette: \_\_\_\_\_
- Don't know / Don't remember.

B6. Which of the following phrases best characterizes you at this time? *(Please mark only one response.)*

- Normal, no complaints, no symptoms of disease
- Able to carry on normal activity, minor symptoms of disease
- Normal activity with effort, some symptoms of disease
- Care for self, unable to carry on normal activity or to do active work
- Require occasional assistance but able to care for most of personal needs
- Require considerable assistance for personal care
- Disabled, require special care and assistance
- Severely disabled, require continuous nursing care

B7. How many times have you fallen in the last 6 months? \_\_\_\_\_ times

B8. **At any time** since you were first diagnosed with cancer, have you used any of the following complementary and alternative therapies?

	No	Yes	Have you used them in the past year?	
a. Special diets such as mostly vegetarian or low fat	0 	1 	→	0  No    1  Yes
b. Movement or physical therapies such as yoga, tai chi, massage, chiropractic, or electromagnetic therapy	0 	1 	→	0  No    1  Yes
c. High dose or mega vitamins (DO NOT include 1-a-day multivitamins), nutritional supplements, or herbal remedies	0 	1 	→	0  No    1  Yes
d. Homeopathy (small doses of drugs that in a healthy person would produce symptoms like those of the disease)	0 	1 	→	0  No    1  Yes
e. Mind/body therapies such as guided imagery/visualization, biofeedback, meditation, relaxation techniques, hypnosis/hypnotherapy, energy healing, therapeutic touch, or music therapy	0 	1 	→	0  No    1  Yes
f. Oriental therapies such as acupuncture, acupressure, Qigong, or Shiatsu	0 	1 	→	0  No    1  Yes
g. Self-help or support groups (either face-to-face or on the Internet)	0 	1 	→	0  No    1  Yes
h. Psychological therapy or counseling from a psychologist, psychiatrist, social worker, or any other mental health professional	0 	1 	→	0  No    1  Yes
i. Faith healing, laying on of hands, or any other spiritual or religious group experience	0 	1 	→	0  No    1  Yes
j. Personal prayer or personal spiritual healing	0 	1 	→	0  No    1  Yes
k. Other, please specify: _____	0 	1 	→	0  No    1  Yes

**Index of Autonomous Functioning (Authorship/Self-Congruence Subscale):**

Below is a collection of statements about your general experiences. Please indicate how true each statement is of your experiences on the whole. Remember that there are no right or wrong answers. Please answer according to what really reflects your experience rather than what you think your experience should be.

1. My decisions represent my most important values and feelings

1 Not at all true	2 a bit true	3 somewhat true	4 mostly true	5 completely true
-----------------------------	------------------------	---------------------------	-------------------------	-----------------------------

2. I strongly identify with the things that I do

1 not at all true	2 a bit true	3 somewhat true	4 mostly true	5 completely true
-----------------------------	------------------------	---------------------------	-------------------------	-----------------------------

3. My actions are congruent with who I really am

1 not at all true	2 a bit true	3 somewhat true	4 mostly true	5 completely true
-----------------------------	------------------------	---------------------------	-------------------------	-----------------------------

4. My whole self stands behind the important decisions I make

1 not at all true	2 a bit true	3 somewhat true	4 mostly true	5 completely true
-----------------------------	------------------------	---------------------------	-------------------------	-----------------------------

[figure not shown]
[figure not shown]
[figure not shown]
[figure not shown]
5. My decisions are steadily informed by things I want or care about

1 not at all true	2 a bit true	3 somewhat true	4 mostly true	5 completely true
-----------------------------	------------------------	---------------------------	-------------------------	-----------------------------

**The Self Efficacy for Managing Chronic Disease Scale (SEMCD):**

For each of the following questions, please *circle* the number that corresponds with your **confidence** that you can do the tasks regularly at the present time

**How confident are you that you can...**

- |  |                         |  |                      |
|--|-------------------------|--|----------------------|
| 1. Keep the fatigue caused by your disease from interfering with the things you want to do?                                | not at all
confident |    | totally
confident |
| 2. Keep the physical discomfort or pain of your disease from interfering with the things you want to do?                   | not at all
confident |    | totally
confident |
| 3. Keep the emotional distress caused by your disease from interfering with the things you want to do?                     | not at all
confident |    | totally
confident |
| 4. Keep any other symptoms or health problems you have from interfering with the things you want to do?                    | not at all
confident |    | totally
confident |
| 5. Do the different tasks and activities needed to manage your health condition so as to reduce your need to see a doctor? | not at all
confident |  | totally
confident |
| 6. Do things other than just taking medication to reduce how much your illness affects your everyday life?                 | not at all
confident |  | totally
confident |

**Self-Efficacy for Managing Symptoms – Short Form 4a****Please respond to each question or statement by marking one box per row.**

CURRENT level of confidence...					
	I am not at all confident	I am a little confident	I am somewhat confident	I am quite confident	I am very confident
SEMSX010 I can manage my symptoms during my daily activities .....	 1	 2	 3	 4	 5
SEMSX014 I can keep my symptoms from interfering with relationships with friends and family .....	 1	 2	 3	 4	 5
SEMSX009 I can manage my symptoms in a public place .....	 1	 2	 3	 4	 5
SEMSX011 I can work with my doctor to manage my symptoms .....	 1	 2	 3	 4	 5

**Perceived Stress Scale**

Instructions: The questions in this scale ask you about your feelings and thoughts during the past 7 days. In each case, please indicate with a check how often you felt or thought a certain way.

1. In the past 7 days, how often have you felt that you were unable to control the important things in your life?

0=never  
 1=almost never  
 2=sometimes  
 3=fairly often  
 4=very often

2. In the past 7 days, how often have you felt confident about your ability to handle your personal problems?

0=never  
 1=almost never  
 2=sometimes  
 3=fairly often  
 4=very often

3. In the past 7 days, how often have you felt that things were going your way?

0=never  
 1=almost never  
 2=sometimes  
 3=fairly often  
 4=very often

4. In the past 7 days, how often have you felt difficulties were piling up so high that you could not overcome them?

0=never  
 1=almost never  
 2=sometimes  
 3=fairly often  
 4=very often

**PROMIS-29:**

Please respond to each question or statement by marking one box per row.

	Physical Function	Without any difficulty	With a little difficulty	With some difficulty	With much difficulty	Unable to do
1	Are you able to do chores such as vacuuming or yard work? .....	 5	 4	 3	 2	 1
2	Are you able to go up and down stairs at a normal pace? .....	 5	 4	 3	 2	 1
3	Are you able to go for a walk of at least 15 minutes? .....	 5	 4	 3	 2	 1
4	Are you able to run errands and shop? .....	 5	 4	 3	 2	 1
	Anxiety In the past 7 days...	Never	Rarely	Sometimes	Often	Always
5	I felt fearful .....	 1	 2	 3	 4	 5
6	I found it hard to focus on anything other than my anxiety .....	 1	 2	 3	 4	 5
7	My worries overwhelmed me .....	 1	 2	 3	 4	 5
8	I felt uneasy .....	 1	 2	 3	 4	 5
	Depression In the past 7 days...	Never	Rarely	Sometimes	Often	Always
9	I felt worthless .....	 1	 2	 3	 4	 5
10	I felt helpless .....	 1	 2	 3	 4	 5
11	I felt depressed .....	 1	 2	 3	 4	 5
12	I felt hopeless .....	 1	 2	 3	 4	 5

	Fatigue During the past 7 days...	Not at all	A little bit	Somewhat	Quite a bit	Very much
13	I feel fatigued .....	 1	 2	 3	 4	 5
14	I have trouble starting things because I am tired .....	 1	 2	 3	 4	 5
	Fatigue In the past 7 days...	Not at all	A little bit	Somewhat	Quite a bit	Very much
15	How run-down did you feel on average? ...	 1	 2	 3	 4	 5
16	How fatigued were you on average? .....	 1	 2	 3	 4	 5

	Sleep Disturbance In the past 7 days...		Very poor	Poor	Fair	Good	Very good					
17	My sleep quality was .....		 5	 4	 3	 2	 1					
18	My sleep was refreshing. ....		 5	 4	 3	 2	 1					
19	I had a problem with my sleep .....		 1	 2	 3	 4	 5					
20	I had difficulty falling asleep .....		 1	 2	 3	 4	 5					
	Ability to Participate in Social Roles and Activities In the past 7 days...		Not at all	A little bit	Somewhat	Quite a bit	Very much					
21	I have trouble doing all of my regular leisure activities with others .....		 5	 4	 3	 2	 1					
22	I have trouble doing all of the family activities that I want to do .....		 5	 4	 3	 2	 1					
23	I have trouble doing all of my usual work (include work at home) .....		 5	 4	 3	 2	 1					
24	I have trouble doing all of the activities with friends that I want to do .....		 5	 4	 3	 2	 1					
	Pain Interference In the past 7 days...		Not at all	A little bit	Somewhat	Quite a bit	Very much					
25	How much did pain interfere with your day to day activities? .....		 1	 2	 3	 4	 5					
26	How much did pain interfere with work around the home? .....		 1	 2	 3	 4	 5					
27	How much did pain interfere with your ability to participate in social activities? .		 1	 2	 3	 4	 5					
28	How much did pain interfere with your household chores? .....		 1	 2	 3	 4	 5					
	Pain Intensity In the past 7 days...											
29	How would you rate your pain on average? .....	 0	 1	 2	 3	 4	 5	 6	 7	 8	 9	 10
	No pain								Worst imaginable pain			

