### 5.2.3 Health outcomes

- 5.2.3.1 Psychological stress [Perceived Stress Scale, 4-item]
- 5.2.3.2 Symptoms [PROMIS Profile 29]
- 5.2.3.3 Health behaviors [items on tobacco use, physical activity, use of CHA]

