### 9.2 Analysis of Secondary Objectives

To meet Objective 2.2.1, we will use descriptive statistics to summarize participant ratings of acceptability.

Descriptive statistics (means, standard deviations, 95% confidence intervals) will be used to summarize proximal outcomes and change in health outcomes by assessment measure to meet Objective 2.2.2. The primary interest will be in estimating the variance for use in planning future studies.

For Objective 2.2.3, the internal study team will work with external collaborators through an iterative process to facilitate a qualitative content analysis of the large quantity of textual MAP data. Specifically, we will first enter text data from the completed paper maps into a software program co-developed by [name] (external Senior Programmer, University of North Carolina-Chapel Hill Renaissance Computing Institute) and [name] (Consultant) using the *ssm* function to create a digital map. [name] will translate the text MAP data into lists that can be sorted by the study team (using the *sort* program). The *sort* program will allow us to group and code similar terms or concepts. Next, we will send our *sort* files back to [name] and he will use Python programming language to help aggregate the large amounts of textual

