12	I felt hopeless .....	 1	 2	 3	 4	 5
	Fatigue During the past 7 days...	Not at all	A little bit	Somewhat	Quite a bit	Very much
13	I feel fatigued .....	 1	 2	 3	 4	 5
14	I have trouble starting things because I am tired .....	 1	 2	 3	 4	 5
	Fatigue In the past 7 days...	Not at all	A little bit	Somewhat	Quite a bit	Very much
15	How run-down did you feel on average? ...	 1	 2	 3	 4	 5
16	How fatigued were you on average? .....	 1	 2	 3	 4	 5

	Sleep Disturbance In the past 7 days...	Very poor	Poor	Fair	Good	Very good						
17	My sleep quality was .....	 5	 4	 3	 2	 1						
18	My sleep was refreshing. ....	 5	 4	 3	 2	 1						
19	I had a problem with my sleep .....	 1	 2	 3	 4	 5						
20	I had difficulty falling asleep .....	 1	 2	 3	 4	 5						
	Ability to Participate in Social Roles and Activities In the past 7 days...	Not at all	A little bit	Somewhat	Quite a bit	Very much						
21	I have trouble doing all of my regular leisure activities with others .....	 5	 4	 3	 2	 1						

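### PROMIS-29 sleep items 18–20 have no response anchors of their own, and items 19–20 are scored against the direction of the header printed above them

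*Combined protocol and SAP*

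**What the plan says.** Section 5.2.3 lists "Symptoms [PROMIS Profile 29" as a health outcome. For Objective 2.2.2, Section 9.2 plans means, standard deviations, confidence intervals and changes, and adds: "The primary interest will be in estimating the variance for use in planning future studies".

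The instrument is printed twice in Appendix F, in the Baseline and the Follow-Up Questionnaire, under the instruction "Please respond to each question or statement by marking one box per row". In each copy the Sleep Disturbance block has a single header row: *Very poor, Poor, Fair, Good, Very good*. No other header appears before the social roles block. The four items are:

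- item 17, "My sleep quality was", boxes 5, 4, 3, 2, 1;
- item 18, "My sleep was refreshing", boxes 5, 4, 3, 2, 1;
- item 19, "I had a problem with my sleep", boxes 1, 2, 3, 4, 5;
- item 20, "I had difficulty falling asleep", boxes 1, 2, 3, 4, 5.

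Neither the protocol text nor the forms state how the sleep items are combined or whether any are reverse-coded.

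**The concern.** A poor-to-good scale does not answer items 18–20, which are statements asking how far something was true. For items 19 and 20 the problem goes beyond wording. Under the printed header, *Very poor* carries 5 (most disturbance) on items 17–18 but 1 (least disturbance) on items 19–20. The two pairs then cancel in a total.

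Respondents have little means of correcting this themselves. The baseline instructions ask them not to skip questions or write in answers outside the choices given, and Section 5.0 allows remote completion, where staff may not be at hand.

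At stake is the sleep domain's mean, its change over two weeks, its rural–urban comparison, and the variance that Section 9.2 wants for planning. With 24 participants, a few divergent readings would move all of these.

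**Working it through.** **Inputs.** The header and box values are those printed in Appendix F and are identical in the baseline and follow-up copies. The score is taken as the raw sum of the four printed boxes. This is an assumption, because the documents give no rule. The plan states no figure to reproduce.

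**Formula.** Let c be the column marked, from 1 (*Very poor*) to 5 (*Very good*). Items 17 and 18 score 6 − c, and items 19 and 20 score c. Then

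score = (6 − c17) + (6 − c18) + c19 + c20 = 12 + (c19 + c20) − (c17 + c18).

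**Same column on all four items, compared with a consistent respondent under an extent header.** The extent header is the *Not at all* to *Very much* row printed for Fatigue and Pain Interference in the same forms. It is applied here to items 18–20 with the box values unchanged.

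| Sleep level | Same printed column throughout | Extent header on items 18–20 |
|---|---|---|
| Very poor | 5+5+1+1 = 12 | 5+5+5+5 = 20 |
| Poor | 4+4+2+2 = 12 | 4+4+4+4 = 16 |
| Fair | 3+3+3+3 = 12 | 3+3+3+3 = 12 |
| Good | 2+2+4+4 = 12 | 2+2+2+2 = 8 |
| Very good | 1+1+5+5 = 12 | 1+1+1+1 = 4 |

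The existing box values are therefore coherent under an extent header. Under the printed one, a gap of 20 − 4 = 16 points between the worst and best sleeper becomes 0, an error of 20 − 12 = 8 or 12 − 4 = 8 points at either end.

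**Other patterns.** There are 5 × 5 × 5 × 5 = 625 possible patterns. The total is 12 exactly when c19 + c20 = c17 + c18. A pair of items reaches the sums 2 to 10 in 1, 2, 3, 4, 5, 4, 3, 2 and 1 ways, so the number of such patterns is 1+4+9+16+25+16+9+4+1 = 85, or 85/625 = 13.6%. The remaining totals lie between 4 and 20. Moving one item by one column from a uniform answer gives 11 or 13. *Very poor* on items 17–19 with *Very good* on item 20 gives 5+5+1+5 = 16.

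**Dependence on reading.** A very poor sleeper who takes the header literally marks column 1 throughout and scores 12. One who treats items 19–20 as degree of agreement from left to right marks column 5 on those two and scores 5+5+5+5 = 20. The sleep is the same and the scores differ by 8 points.

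**Item 18.** Its values run 5 to 1, so *Very poor* means more disturbance, as in item 17. Only its wording misfits; the conflict in scoring direction is confined to items 19–20.

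**The case against.** The strongest objection is that the fielded form may be sound. A table row can drop out when a PDF is converted to text, and both copies share one layout, so they are not independent evidence. Section 8.0 places patient-reported outcomes in REDCap, whose screens are not in the documents. Box values that make sense under an extent header fit a lost row as well as a misprint.

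This stands as a reason to check first, though a lost row is unlikely. The header is absent from both copies, while the repeated Fatigue header above item 15 ("How run-down did you feel on average") survives in both. The forms also contain other assembly slips: the follow-up stress scale numbers two items 4, and the follow-up smoking section skips to a question B6 that the form does not have.

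A reader might go further and infer that anyone using the printed anchors scores 12 regardless of sleep, so that the SD and change are necessarily 0. The documents do not support that. The result of 12 needs equal column sums for the two item pairs, and a zero SD and zero change would need every participant to answer that way at both visits. Nor do they support discarding data already collected, since the form actually used has not been seen.

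Finally, this is one four-item block of a secondary instrument in a single-arm pilot. That is right, and it limits the weight of the point.

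**Conclusion.** The concern holds in limited form. As printed in both questionnaires, items 18–20 lack suitable anchors, and items 19–20 are scored in the opposite direction to items 17–18. Assuming a raw sum, consistent answers total 12 at any level of sleep, up to 8 points from the coherent score on a 4–20 range. Other totals depend on how each person reads the header. The distortion of the SD has no predictable direction: uniform answers shrink it, while mixed readings add variation unrelated to sleep.

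The effect is confined to the sleep domain of PROMIS-29 under Sections 5.2.3.2 and 9.2. The enrollment, participation and retention rates of Section 5.1 and the sample-size reasoning of Section 9.3 are untouched. The conclusion rests on the printed layout being the one fielded, which remains to be confirmed.

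**What to change.** 1. Compare the fielded paper forms and the REDCap build with the source instrument, for baseline and follow-up.
2. If the header is missing there, print a separate row above items 18–20 in both forms (*Not at all, A little bit, Somewhat, Quite a bit, Very much*) and keep the existing box values.
3. State the scoring rule for the sleep domain in Section 9.2.
4. Only for participants confirmed to have answered on the faulty layout, do not compute the four-item score; report item 17 alone. Their answers to items 19–20 cannot be recoded reliably because each person's reading is unknown. Item 18 agrees in direction, but what a ticked box meant under ill-fitting anchors is also unknown.

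The cost is one header row in two questionnaires and the matching REDCap screens, a sentence in Section 9.2, and a minor amendment. Participants carry no added burden. If the check finds the fielded form correct, only the appendix needs correcting and no data are lost.

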**Comprehensive Score for Financial Toxicity (COST):**

Below is a list of statements that other people with your illness have said are important. **Please circle or mark one number per line to indicate your response as it applies to the past 7 days.**

		Not at all	A little bit	Somewhat	Quite a bit	Very much
1	I know that I have enough money in savings, retirement, or assets to cover the costs of my treatment.	 0	 1	 2	 3	 4
2	My out-of-pocket medical expenses are more than I thought they would be.	 0	 1	 2	 3	 4
3	I worry about the financial problems I will have in the future as a result of my illness or treatment.	 0	 1	 2	 3	 4
4	I feel I have no choice about the amount of money I spend on care.	 0	 1	 2	 3	 4
5	I am frustrated that I cannot work or contribute as much as I usually do.	 0	 1	 2	 3	 4
6	I am satisfied with my current financial situation.	 0	 1	 2	 3	 4
7	I am able to meet my monthly expenses.	 0	 1	 2	 3	 4
8	I feel financially stressed.	 0	 1	 2	 3	 4
9	I am concerned about keeping my job and income, including work at home.	 0	 1	 2	 3	 4
10	My cancer or treatment has reduced my satisfaction with my present financial situation.	 0	 1	 2	 3	 4
11	I feel in control of my financial situation.	 0	 1	 2	 3	 4

Study ID: \_\_\_\_\_

Date: \_\_\_\_\_

## **Mapping to Guide Self-Management in Cancer Survivors**

### Follow-Up Questionnaire

Study ID: \_\_\_\_\_  
Date: \_\_\_\_\_

Name of Facilitator: \_\_\_\_\_

**Acceptability - Future Study Planning**

1. How important is it for people to have support in determining their own health-related goals following cancer treatment?

1	2	3	4	5	6
Not at all	A little bit	Somewhat	Moderately	Quite a bit	Very much

2. How interested would you be in meeting with someone to follow-up with you on the goals you chose during the study mapping exercise?

1	2	3	4	5	6
Not at all	A little bit	Somewhat	Moderately	Quite a bit	Very much

3. What person would you like to meet with to discuss those goals?

- a. A nurse
- b. Other healthcare provider
- c. A mental health provider
- d. A cancer survivor
- e. Any of the above people
- f. Other (please specify): \_\_\_\_\_

4. How often do you think it would be helpful to meet with someone to discuss your goals?

- a. Weekly
- b. Twice per month
- c. Monthly
- d. I do not think it would be helpful
- e. Other (please specify): \_\_\_\_\_

5. How would you like to meet with someone to discuss your goals?

- a. In person at the Cancer Center
- b. In person at my primary healthcare location
- c. On the telephone
- d. Over videoconferencing
- e. I would not like to meet with someone
- f. Other (please specify): \_\_\_\_\_

